Population	
Inclusion criteria for part 1 and 2:
 
 • Patients aged ≥ 18 years old • Patients with histologically/cytologically confirmed renal cell carcinoma (International Classification of Disease 10.revision (ICD)-10 C64) • Full medical information regarding all treatments before, during and after 1L should be available. 
Specific inclusion criteria only for Part 1:
 
 • Patients with locally advanced or metastatic disease and a start of any systemic 1L therapy against RCC between 01 January 2020 and 31 December 2021 
Specific inclusion criteria only for Part 2:
 
 • Patients with locally advanced or metastatic disease, who were treated with a combination of ICI + TKI or ICI + ICI as 1st line therapy against RCC and who had a completion of this therapy between 01 January 2020 - 31 December 2021 with a follow-up period of at least 3 months after completion of the 1L. 
Exclusion criteria for part 1 and 2:
 
 • Patients participating in an interventional clinical study within 30 days before start of 1L.
Outcomes	
The following clinical outcomes are of relevance in the study and should be answered regarding the research questions:
 
Primary Outcome
 
 ○ Progression-free survival in 1L in median and at defined timepoints after start 
Secondary outcomes

	
○ Overall survival rates from start of 1L therapy, expressed as median and at pre-defined timepoints○ Proportions of different therapy protocols used in 1L○ Best responses to 1L therapies○ Duration of response to 1L therapies○ Time-to-progression to 1L therapies○ Time-to-next-therapy to 1L therapies○ Frequency of modifications and discontinuations in 1L○ Reasons for modifications and discontinuations in 1L○ Treatment continuation after modifications and discontinuations in 1L (for all therapies and in relation to specific protocols like axitinib + avelumab or nivolumab + ipilimumab) 
Other Outcomes
 
○ Distribution of 1L therapy by age, gender and risk rating○ Distribution of 1L therapy and frequency of modifications/discontinuations by medical speciality and institution

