	
 ▪ Defined as median and rates of patients alive at pre-defined timepoints (12 and 18 months) after start of 1L therapy. ○ Proportion of different drug regimen in 1L 
 ▪ Defined as percentages of therapy protocols used as 1L therapy. ○ Best response rate (RR) in 1L 
 ▪ Defined as best response (complete response (CR) / partial response (PR) / stable disease (SD) / progressive disease (PD) / not done (ND)) recorded from the start of the therapy until disease progression/recurrence based on investigator's assessment. A confirmation of response is not required. ○ Duration of Response (DoR) in 1L 
 ▪ Defined as time from documentation of first disease response to disease progression. ○ Time to progression (TTP) in 1L 
 ▪ Defined as time from start of therapy until objective disease progression without including deaths. ○ Time to next treatment (TTNT) in 1L 
 ▪ Defined as time from last drug administered to initiation of next therapy. ○ Dose modifications and discontinuations in 1L 
 ▪ Defined of number of patients with at least 1 dose modification (reduction of dose or cancelling of administration) or with an interim/permanent discontinuation of one or all drugs of a therapy. ○ Handling after dose modification or discontinuations in 1L 
 ▪ Defined as continuation of therapies after dose modifications or temporary/permanent discontinuation of single drugs. 
The clinical outcomes will be analyzed for the total group of all patients and for following subgroups:
 
 ○ Age: < 70 years vs. ≥70 years ○ Gender: male vs. female ○ Risk rating: favorable (low) vs. intermediate vs poor (high) risk ○ Medical disciplines: urology vs. medical oncology ○ Institutions: practices vs. hospitals
Milestones	
Planned milestones:
 
 ● Start of data collection: 1 October 2022 ● Interim analysis (expected): 31 October 2022 ● End of data collection: 30 January 2023 ● Final study report: 15 April 2023

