8.1. Primary Research Questions

Based on the above background, there are currently a number of unanswered questions for health services research:

- How is the effectiveness, defined as measurement of beneficial effects under “real world” clinical settings, (e.g. progression-free survival, overall survival and best response) of TKI and/or ICI as 1L in patients with aRCC?
- How are patients with aRCC treated in 1L under daily care conditions in Germany in general and in accordance to medical specialities (urology and medical oncology) and treatment settings (hospitals vs office-based practices)?
- Are all patients assigned to individual risk ratings under standard daily care conditions according to a scale developed by the IMDC before start of a 1L?
- How are patients treated in 1L in different risk rating groups and how is the adherence to national/international guidelines?
- What kind of previous and subsequent therapies are administered before and after 1L?
- How often are evaluations for PD-L1 expression performed before start of 1L and how many patients are positive (TPS $\geq 1\%$) or negative?

- How long are patients treated with TKI + ICI and ICI + ICI in 1L in general and in relation to specific therapies like avelumab + axitinib?
- How frequent are dose modifications and early discontinuations and what are the reasons?
- Are there differences in the handling of modifications among medical disciplines?

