9.1.1. Inclusion criteria

Patients must meet all of the following inclusion criteria to be eligible for inclusion in the study:

Part 1 and 2:

- Patients aged ≥ 18 years old
- Patients with histologically/cytologically confirmed renal cell carcinoma (ICD-10 C64)
- Full medical information regarding all treatments before, during and after 1L should be available.

Specific inclusion criteria only for Part 1:

- Patients with locally advanced or metastatic disease and a start of any systemic 1L therapy against RCC between 01 January 2020 and 31 December 2021

Specific inclusion criteria only for Part 2:

- Patients with locally advanced or metastatic disease, who were treated with a combination of ICI + TKI or ICI + ICI as 1L therapy against RCC and who had a completion of this therapy between 01 January 2020 - 31 December 2021 with a follow-up period of at least 3 months after completion of the 1L.

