9.2. Variables

The following variables will be captured by a specific eCRF and are needed for the analysis of all outcomes and for answering all research questions.

Tab. 2: List of all variables, role, data source and operational definitions

Variable	Role	Data source(s)	Operational definition
Age and gender	baseline characteristic	Medical Chart	Years; male/female
Weight and body surface	baseline characteristic	Medical Chart	kg, m ²
Date of first diagnosis	baseline tumor characteristic	Medical Chart	dd/mm/yyyy
Stage and risk rating (IMDC) at first diagnosis and at start of 1L	baseline tumor characteristic	Medical Chart	Favorable risk / intermediate risk / poor risk
Assessments and results of PD-L1 expression as TPS	baseline tumor characteristic	Medical Chart	y/n; 0-100%
Non-medicinal pre-treatments (primary OP, cytoreductive nephrectomy radiotherapy)	baseline tumor characteristic	Medical Chart	y/n; dd/mm/yyyy of OP; mode of OP; intention of OP (curative/palliative); period and dose of radiotherapy
Medicinal pre-treatments (adjuvant, neoadjuvant)	baseline tumor characteristic	Medical Chart	y/n; start/stop and used therapy protocol
Location of administration and performing medical discipline	Relevant for outcomes	Medical Chart	Urological practice; hematological practice; hospital with urological department; hospital with oncological department
Administered drugs / protocols in 1L	Relevant for outcomes	Medical Chart	administered therapy protocol
If applicable: Reason for ineligibility of ICI	Relevant for outcomes	Medical Chart	Concomitant disease; patient's wish
Duration of 1L	Relevant for outcomes	Medical Chart	Start/stop of therapy or every cycle;

Dates of administrations for i.v. drugs in 1L	Relevant for outcomes	Medical Chart	Dates of every administration
Dosages per administration	Relevant for outcomes	Medical Chart	Dose of administered drugs per administration
Dose modifications or drug administration cancelling or interim/permanent discontinuations of single drugs / complete therapy in 1L	Relevant for outcomes	Medical Chart	Each for single/all drugs: Dose modification; cancelling single administration; temporare discontinuation; permanent discontinuation
Reasons for modifications, cancelling of single administrations and discontinuations in 1L	Relevant for outcomes	Medical Chart	Each for single/all drugs: intolerance; age; performance status; patient's decision; other

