Supportive drugs prescribed during 1L	Relevant for outcomes	Medical Chart	Administered supportive drugs in connection with cancer therapy
Date of first response and best response in 1L incl. date and mode of assessment	Relevant for outcomes	Medical Chart	dd/mm/yyyy; CT/MRI/ultrasound/x-ray; clinical assessment; laboratory
Assessment of first and best response in 1L	Relevant for outcomes	Medical Chart	CR/PR/SD/PD/ND
Date of tumor progression	Relevant for outcomes	Medical Chart	dd/mm/yyyy
Reasons for end of 1L	Relevant for outcomes	Medical Chart	Progression; intolerance; decision oncologist; patient's wish; death; deterioration performance
Subsequent therapies (Second-line therapy (2L) and higher) with drugs/protocol and dates for start / end	Relevant for outcomes	Medical Chart	y/n; used drugs/regime; start/stop
Concomitant diseases and therapeutic measures	Relevant for outcomes	Medical Chart	Detailed diagnosis; therapeutic measures OP/medicinal/none/other

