9.7. Quality control

The most relevant step in quality control and quality assurance will be an avoidance of inaccuracies or mismatches in terminology by data entries in data fields over a selection of parameters or descriptions out of pre-defined drop-down-lists. Free text is only intended for descriptions after selection of "other", which will be possible in some data fields, where a pre-definition cannot be

implemented for 100%. For all dates regarding parameters like first diagnosis, pre-treatments, therapy administrations automatic checks are implemented for data entries, so that the course of treatment will be shown correctly (e.g. adjuvant therapy after OP and before palliative therapy, end of 1L before start of 2L, end of therapy after last administration). In defined data fields new explanation fields will open up after selection of specific documentations (e.g. after selection of dose modification query for modified dose, after selection of end of therapy query for reason). In data fields with information like weight, height or age, automatic standard range checks, are implemented to avoid input errors. In addition to these automatic checks every data entry will also be checked by an experienced data manager and, if needed, by the medical lead.

In case of relevant inaccuracy or implausibility, patient's data files will be rejected before further analytical processes will start. After the decision for rejection of patients the investigator will be informed about the reason for rejection and all data will be deleted immediately.

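### Does the end of first-line therapy count as a permanent discontinuation, and which eCRF field gives its reason?

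*Combined protocol and SAP*

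**What the plan says.** The outcome is defined in the Abstract (Data Analysis) as a number of patients: those with at least one dose modification, "or with an interim/permanent discontinuation of one or all drugs of a therapy". The Other Outcomes in the Abstract include the "frequency of modifications/discontinuations by medical speciality and institution".

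Table 2 (section 9.2) supplies the data through two sets of fields:

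- One field records dose modifications, cancelled administrations and "interim/permanent discontinuations of single drugs / complete therapy in 1L". Its reason list begins "Each for single/all drugs: intolerance; age; performance status" and continues with the patient's decision and other.
- A separate field, reasons for end of 1L, begins "Progression; intolerance; decision oncologist" and continues with the patient's wish, death and deteriorating performance.

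Section 9.7 gives the end of therapy its own eCRF prompt: "after selection of end of therapy query for reason". Section 8.1 asks: "How frequent are dose modifications and early discontinuations and what are the reasons". For Part 2, section 9.1.1 admits patients "who had a completion of this therapy between 01 January 2020 - 31 December 2021". Section 9.6 leaves detailed methodology to a separate SAP.

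**The concern.** The definition includes all-drug stops on purpose. The next outcome in the same list, on handling after modification, is limited to discontinuation of single drugs, while this one covers one or all. Every course of 1L that has ended has, in a literal sense, been permanently discontinued. Neither the outcome definition nor the objective in section 8.2 excludes an end for progression or death. The qualifier early appears only in the research question and is not defined; completion is not defined either.

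Two things could go wrong:

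- **The frequency.** If the end of 1L counted, the Part 2 figure would be fixed by eligibility and would say nothing about tolerability, which section 7 names as a particular emphasis.
- **The reasons.** One stop of the whole therapy could be coded from either of two lists, and no rule says which prevails. If sites differed in the field they used, part of a difference between urology and oncology, or between practices and hospitals, could come from form use and not from practice.

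**Working it through.** The plan states no figure on this point, so the check compares the fields and follows each kind of stop through them.

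**1. The two reason lists (Table 2, section 9.2)**

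| Reason | Discontinuation field | End-of-1L field |
|---|---|---|
| Intolerance | yes | yes |
| Performance status / deterioration | yes | yes |
| Patient's decision / wish | yes | yes |
| Age | yes | no |
| Other | yes | no |
| Progression | no | yes |
| Oncologist's decision | no | yes |
| Death | no | yes |

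The lists have 5 and 6 options, of which 3 match (one word for word, two in substance). Only in the first: 5 − 3 = 2. Only in the second: 6 − 3 = 3. Distinct reasons: 3 + 2 + 3 = 8.

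**2. Where the fields overlap**

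- *End of 1L for progression or death.* Only the end-of-1L list names these. The discontinuation list could take them only under other, so they belong in the end-of-1L field.
- *Temporary stop of all drugs.* This is not an end of 1L and belongs only in the discontinuation field. It gives the words on complete therapy in that field a use that does not overlap.
- *Permanent stop of one drug in a combination.* Discontinuation field only.
- *Permanent stop of all drugs for another reason, such as intolerance.* This fits both fields, and it is the real overlap.

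**3. The literal reading**

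Part 2 is planned with 300 patients, all with completed 1L. If every end of 1L counted, the result would be 300/300 = 100% before any chart was opened. Such an outcome could not answer the question in section 8.1 about early discontinuations, and the separate end-of-1L variable would have no purpose beside it. Sections 7 and 9 also present discontinuation as a way of handling intolerability. The reading that agrees with the rest of the protocol leaves out ends for progression and death.

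**4. What an analyst can do with the data collected**

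For each patient the form holds the type of discontinuation by drug and its reason, the end-of-1L reason, the start and stop of therapy, and the date of progression. A workable rule is: count a patient if the discontinuation field records a temporary or permanent stop other than an end of 1L for progression or death, or if the end-of-1L field gives a reason other than those two. Because the outcome is a number of patients, a stop entered in both fields counts once. A stop entered only at the end of 1L is still captured. Under this rule the count does not depend on which of the two fields a site used.

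For the reason table, three of the eight reasons map directly between the lists and the other five each appear on one list only. A choice is needed only when both fields are filled for the same stop and the reasons differ. The protocol gives no figure from which the frequency of that can be derived.

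**The case for a change.** The strongest contrary case is practical. Sections 9.3 and 9.5 make the data fully anonymous, and section 9.3 says that queries cannot be submitted, so conflicting entries cannot be clarified later. An analysis rule does not tell sites which field to use, and data collection was planned to start on 1 October 2022 with an interim report on 31 October 2022. Deferring methods to a SAP does not show that the SAP contains the rule. Frequency and reasons of discontinuation are a stated secondary objective.

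Part of this stands. No written precedence exists for conflicting reasons, and a sentence in the SAP would do no harm. It does not carry the point further, for three reasons:

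- Separating progression and death from other stops needs no query, because the reasons are already on the form.
- Nothing in the protocol suggests that specialities or institutions would use the fields differently. Section 9.7 describes drop-down lists, automatic checks and a data manager's review of every entry. These do not supply the missing rule, but they make unchecked variation between sites less likely.
- The obvious instruction, to send every all-drug stop to the end-of-1L field alone, creates gaps of its own. That list has no code for age or other. For TKI monotherapy in Part 1, a stop of the single drug is also a stop of all drugs, so the instruction would not separate the two fields.

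**Conclusion.** No change to the plan is called for. The wording gap is real: the outcome definition does not mention the end of 1L, and a permanent stop of all drugs for a reason other than progression or death fits two fields whose lists share 3 of 8 reasons. The intended meaning can still be recovered from the protocol, the literal 100% in Part 2 is not a plausible reading, and the data needed for a sensible count are collected. The remaining choice, which reason to show when two entries conflict, is ordinary SAP detail for one descriptive secondary outcome. No effect is shown on the primary outcome (progression-free survival), on the sample sizes of 400 and 300, or on any stated result.

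This rests on three assumptions: that the end-of-1L reason is filled in for patients whose therapy has ended, as the prompt in section 9.7 implies; that other in the discontinuation list is not routinely used for progression; and that the analyst reads both fields together.

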Variables	For the evaluations of the mentioned clinical outcomes the following parameters will be captured: Part 1: 
○ Demographic data (age, gender, weight, body surface)○ Date of first diagnosis○ Stage and risk rating (IMDC) at first diagnosis and at start of 1L○ Assessments and results of PD-L1 expression○ Non-medicinal pre-treatments (primary operation (OP), cytoreductive nephrectomy, radiotherapy)○ Medicinal pre-treatments (adjuvant, neoadjuvant)○ Location of administration and performing medical discipline○ Administered drugs / protocols in 1L○ If applicable: Reason for ineligibility of ICI○ Dates of administrations for i.v. drugs in 1L○ Duration of 1L treatment○ Dosages per administration○ Dose modifications or drug administration cancelling or interim / permanent discontinuations of single drugs / complete therapy in 1L○ Reasons for modifications, cancelling of single administrations and discontinuations in 1L○ Supportive drugs prescribed during 1L○ Date of first response and best response to 1L incl. date and mode of assessment

- Assessment of first and best response in 1L
- Date of tumor progression
- Reasons for end of 1L
- Subsequent therapies (2L and higher) with drugs/protocol and dates for start / end
- Concomitant diseases and therapeutic medications

Part 2:

If patients will qualify for part 1 and part 2 (completion of 1L and follow-up of at least 3 months after completion), the documented data from part 1 will be transferred to part 2 automatically, so that only additional parameters must be filled in. If patients are newly documented in part 2, all of the parameters have to be documented.

- Demographic data (age, gender, weight, body surface)
- Date of first diagnosis
- Stage and risk rating (IMDC) at first diagnosis and at start of 1L
- Assessments and results of PD-L1 expression as TPS
- Non-medicinal pre-treatments (primary OP, cytoreductive nephrectomy, radiotherapy)
- Medicinal pre-treatments (adjuvant, neoadjuvant)
- Location of administration and performing medical discipline
- Administered drugs / protocols in 1L
- If applicable: Reason for ineligibility of ICI
- Dates of administrations for i.v. drugs in 1L
- Dosages per administration
- Dose modifications or drug administration cancelling or interim /permanent discontinuations of single drugs / complete therapy in 1L
- Reasons for modifications, cancelling of single administrations and discontinuations in 1L

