9.3. Data sources

Source documents (paper or electronic medical charts) are those, in which patient data of daily care are recorded and documented in individual patient files. The data to be collected in the study will be obtained via a specific programmed eCRF. The data in the eCRF should be consistent with the relevant source documents. Medical records should contain demographic data, medical data, treatments and diagnostic documentations according to common practice. The documentation will be performed under full anonymization, so that a re-identification of single patients will not be possible. Based on this anonymization, queries for explanations or changes of data could not be submitted by the data

management. All documented variables will be checked by data manager and/or medical lead of GermanOncology in relation to implausibility, inaccuracies or missing data. If implausibility or inaccuracies or missing data of single patients will be of great relevance for analyses, the data management and/or medical lead have the right to reject patients. For such rejected patients no payment will be triggered.

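### The count of patients with dose modifications or discontinuations is not separated from the end of first-line therapy, so in Part 2 it is either everyone or dependent on site coding

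*Combined protocol and SAP*

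**What the plan says.** The Abstract (Data Analysis) counts patients with at least one dose reduction or cancelled administration, "or with an interim/permanent discontinuation of one or all drugs of a therapy". It restricts neither the reason nor the timing.

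A stop of the whole therapy is a recordable event. The Abstract's variable list for Part 1 has "Dose modifications or drug administration cancelling or interim / permanent discontinuations of single drugs / complete therapy in 1L", and the Part 2 list has the same item. Tab. 2 in section 9.2 gives the action codes as "Each for single/all drugs: Dose modification; cancelling single administration; temporare discontinuation; permanent discontinuation". The reasons for these actions begin "Each for single/all drugs: intolerance; age; performance status" and continue with the patient's decision and other.

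Tab. 2 has a separate field for why 1L ended. Its options begin "Progression; intolerance; decision oncologist" and continue with patient's wish, death and worsening performance. Section 9.7 describes an automatic prompt, "after selection of end of therapy query for reason".

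Section 9.1.1 limits Part 2 to patients treated with an ICI combination "and who had a completion of this therapy between 01 January 2020" and 31 December 2021, with at least 3 months of follow-up afterwards. Section 9.3 says that, because of anonymisation, "queries for explanations or changes of data could not be submitted by the data" management.

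Section 8.1 asks about *early* discontinuations. The word is not defined, and it appears neither in the outcome definition nor in the objective in section 8.2.

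**The concern.** Every Part 2 patient has, by the entry rule, stopped the 1L combination. If a permanent stop of all drugs counts whatever its reason, every Part 2 patient has the outcome. If it does not always count, the plan has to say when it does, and it does not.

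Section 7 places particular emphasis on how intolerabilities are handled under combination therapy, which is the Part 2 population. The Abstract lists modifications and discontinuations by medical speciality and institution among its outcomes. A count fixed at 100% cannot differ between groups. A count that follows documentation habits can differ between groups for reasons unrelated to care.

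**Working it through.** The plan gives no expected value for this outcome. Its one calculated figure, n = 370, concerns PFS rates. It reproduces: 1.96² × 0.25 × 10,000 / (1.96² × 0.25 + 0.05² × 9,999) = 9,604 / 25.958 = 369.98. It has no bearing here. The Part 2 size of 300 is stated in section 9.4 without a calculation.

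1. **Literal reading.** All drugs have been stopped in every Part 2 patient (section 9.1.1), and a permanent stop of all drugs is counted (Abstract). Result: 300 of 300. Part 1 requires only a start of 1L, so patients still on treatment can keep the figure below 100% there.

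2. **Narrower reading.** Four features suggest it: the word *early* in section 8.1, an action-reason list without progression or death, a separate end-of-1L field, and a separate end-of-therapy prompt in section 9.7. Two cases show what is left open:
   - A patient stops both drugs on progression. Site A enters only the end of 1L, with reason progression, and the patient is not counted. Site B also enters a permanent discontinuation of all drugs, with reason other, and the patient is counted. Both comply with the text.
   - A patient stops both drugs for intolerance. Site A enters this only as the end of 1L, and a count taken from the action field misses it. Site B enters both fields. Intolerance, performance and the patient's own choice appear in both reason lists, so either entry is natural.

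3. **Discontinuation component, for scale.** Section 8 quotes adverse-event-driven discontinuation from 8% (both drugs, avelumab + axitinib) to 37.2% (either or both drugs, pembrolizumab + lenvatinib). Times 300, that is 24 to 112 patients, against 300 under the literal reading. If a share s of patients is at sites that code every end of 1L as a discontinuation, and d is the true rate, the count is 300 × (s + (1 − s) × d). The share is not in the document. For an assumed s of 0.25 to 0.75, the count runs from 300 × (0.25 + 0.75 × 0.08) = 93 to 300 × (0.75 + 0.25 × 0.372) = 253.

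4. **Composite, for scale.** Interruptions and reductions count anyway, so fewer patients can change status:

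| Regimen | Component quoted in section 8 | Already counted of 300 | Can still change |
|---|---|---|---|
| Avelumab + axitinib | 42% (axitinib reduction) | 126 | at most 174 |
| Pembrolizumab + axitinib | 69.9% (interruption) | 210 | at most 90 |
| Pembrolizumab + lenvatinib | 78.4% (interruption) | 235 | at most 65 |

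The nivolumab + ipilimumab figure (delays in up to 58%) is an upper value, so it gives no such limit. The 42% is an incomplete floor, because section 8 gives no interruption rate for that regimen. Each row treats all 300 patients as if they had one regimen, although section 9.1.2 sets quotas across regimens. These are trial rates, used for scale only.

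**The case against.** The strongest reply is that a later SAP can settle this. Section 9.6 leaves detailed methods to a SAP, and the document reviewed contains no SAP section. The reason for end of 1L is collected in its own field, so one derivation rule at analysis would make the count of whole-therapy stops independent of what sites entered as an action. That stands. A reader might infer from the ban on queries that the rule has to be in place before data collection starts. The document does not support that, because no entry needs correcting.

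It can also be said that nobody intends completion of therapy to count as a discontinuation, and that most of the information survives. Both points have force. The cues in working step 2 favour the narrower meaning. The action types, their reasons, the comparison of reduction with cancelling (section 8.2) and the handling of single-drug stops (Abstract) are separately recorded or planned. But the narrower meaning is not written down, and the composite as written does not use it.

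A reader might further infer a definite false difference between practices and hospitals. Take the 65:35 split of section 9.4 (195 and 105 patients) and a true composite of 69.9% in both. If practices code half of the remaining final stops as discontinuations and hospitals none, the result is 85.0% vs 69.9%: 15.1 points, against a 95% half-width of 1.96 × √(0.8495 × 0.1505/195 + 0.699 × 0.301/105) = 10.1 points. If hospitals code a quarter instead, it is 84.9% (0.8495) vs 77.4%: 7.5 points against 9.4. The answer turns on coding shares that are not in the document. The 65:35 split is itself justified there by most therapies being oral, whereas Part 2 takes only ICI combinations. This is illustration, not an estimate.

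**Conclusion.** The concern holds in a limited form. As written, the Part 2 composite is 300 of 300. Under the probably intended meaning it depends on whether the end of 1L is also entered as a permanent discontinuation. The literal result needs only the outcome definition and the Part 2 entry rule; it rests on no assumed rate.

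The damage is to the Part 2 composite and discontinuation count and to their comparison by discipline and institution. It does not reach the other recorded components, the reasons, or the primary PFS outcome, and Part 1 is less exposed. The size of any coding effect cannot be derived from the document; the figures in working steps 3 and 4 rest on pivotal-trial rates and, in step 3, an assumed coding share. The outcome is secondary and descriptive, but the plan gives it weight and the repair is cheap, so it should be made.

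**What to change.** In the outcome definition or in the SAP, replace the single composite with separate patient counts:

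- (a) dose reduction;
- (b) cancelled administration;
- (c) interim discontinuation of one or all drugs;
- (d) permanent stop of one drug with the other continued;
- (e) permanent stop of all drugs for a reason other than progression or death.

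Derive (e) centrally from the reason for end of 1L in Tab. 2, whatever was entered in the action field. Show each count by recorded reason, with intolerance and missing as rows of their own. State that an end of 1L for progression or death is not a discontinuation event. The all-reason objective in section 8.2 is kept, with the intolerance-only figure beside it.

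The cost is a definition change; the fields are already collected. A one-line eCRF instruction before data collection is desirable but not essential. The drawback is reliance on the charted reason. The end-of-1L list has no option for other reasons or for completion as planned, so planned stops may fall under the physician's decision or be missing. Footnote this, or add an option if the eCRF is still open. Leaving out deaths should change little in Part 2, since entry already requires 3 months of follow-up after 1L.
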